10.2.2.6 Telephone follow-up post-op

Telephone follow-up will be performed at 6 weeks, 3, 4.5 and 9 months after the operation to ensure that the subject is not lost to follow-up between two visits, and to collect adverse events in time. The subject may choose to receive an imaging examination during his/her follow-up visit to the

Confidential and Proprietary

This document contains confidential and proprietary information on Smith & Nephew PLC and Smith & Nephew, Inc. and is only available to Smith & Nephew and its manufacturers. Without prior written approval of Smith & Nephew, the content cannot be replicated, printed totally/partially or disclosed in any other way, and anyone must use it as per the requirements, either expressed or implied by Smith & Nephew.

Study Protocol - Device	Smith+Nephew
A Prospective, Multi-center, Randomized Clinical Study to Evaluate the Safety and Effectiveness of Biosure Regenesorb Interference Screw in Arthroscopic Reconstruction of Cruciate Ligaments in Chinese Patients	Study No.: BIOSURE RG.SMD.PMA.2019.01
	Version: V2.0/July 3rd, 2020
	Page 39 of 74

hospital 3 months after the operation. The follow-up information should be recorded in the medical record of the subject. Please refer to Study Visit Schedule for the acceptable follow-up windows.

Collect and record any AE since last visit and necessity for re-operation.

At one week prior to each follow up visit after the operation, the Clinical Research Coordinator will call the subject to confirm the appointment. During the contact with the subject, if any change of subject contact information is observed, e.g. address, phone number, then the corresponding contact information in the subject's medical file should be updated as well.

10.2.2.7 Unscheduled Visits

All information obtained during an unscheduled visit should be recorded in the source documents and on the appropriate CRF. .

10.2.2.8 Laboratory examinations

The laboratory examinations required to be performed include:

- Blood routine examination: Haemoglobin, Platelet count, WBC count, neutrophil count, erythrocyte sedimentation rate
- Coagulation examination: Prothrombin time (PT), activated partial thromboplastin time (APTT), thrombin time (TT), fibrinogen (FIB)
- Biochemical examination: Urea or urea nitrogen, creatinine, AST (SGOT), ALT (SGPT), blood glucose
- C-reactive Protein
- Pregnancy test: females at a child-bearing age only

10.2.2.9 Imaging examination

Take X-ray films, CT images and MRI images of the knee joint pre-operation, intraoperative-postoperative (Day 0-5) (X-ray film and CT image), 6- and 12- month follow-up after operation, respectively. All imaging observations are to be reported on the CRF. Postoperative device-related and surgical adverse events are to be reported.

Confidential and Proprietary

This document contains confidential and proprietary information on Smith & Nephew PLC and Smith & Nephew, Inc. and is only available to Smith & Nephew and its manufacturers. Without prior written approval of Smith & Nephew, the content cannot be replicated, printed totally/partially or disclosed in any other way, and anyone must use it as per the requirements, either expressed or implied by Smith & Nephew.

Study Protocol - Device	Smith+Nephew
A Prospective, Multi-center, Randomized Clinical Study to Evaluate the Safety and Effectiveness of Biosure Regenesorb Interference Screw in Arthroscopic Reconstruction of Cruciate Ligaments in Chinese Patients	Study No.: BIOSURE RG.SMD.PMA.2019.01
	Version: V2.0/July 3rd, 2020
	Page 40 of 74

Mainly observe bone ingrowth into screw of the absorbable screw after implantation.

X-ray films, CT images and MRI images are taken during the postoperative 24-month follow-up to mainly observe absorption of the absorbable screw after implantation. All imaging observations are reported in CRF.

The specific imaging evaluation requirements will be provided in a separate document to radiologists for evaluation of examination results.

10.2.2.10 Activity limitations

The patients need to self-limit their activities and bear acceptable loads within 6 months after operation. Rehabilitation is recommended 2 weeks after operation until to 3 months. Moderate activities are allowed 4 months after operation. Vigorous exercise is only recommended 6 months after operation.

10.2.3 Device operation specifications

All study-related arthroscopic surgery procedures will be operated according to the surgical technique described in the specifications and IFU.

The physicians participating in this study must skillfully master the arthroscopic surgery procedures for soft tissue repair. In addition, before the investigational device is implanted, all physicians participating in this study must be appropriately trained in the surgical technique and device use.

10.3 Monitoring plan

This study will be monitored by the Sponsor or qualified personnel designated by the Sponsor. The monitor can be employees of the Sponsor, can also come from the contract research organization (the Sponsor's agent). The Sponsor or Sponsor's agent will monitor according to the monitoring frequency and the monitoring contents specified in the monitoring plan.

The Sponsor, Sponsor's agent, EC and regulatory authorities can directly access the source documents, so as to verify and evaluate the clinical data submitted by the investigator to the Sponsor through the CRF.

The investigator is responsible for obtaining and maintaining the integrity of the subject health information (original document) recorded in the medical record. The source data includes all original record information and certified copies of the original records (including clinical findings,

Confidential and Proprietary

This document contains confidential and proprietary information on Smith & Nephew PLC and Smith & Nephew, Inc. and is only available to Smith & Nephew and its manufacturers. Without prior written approval of Smith & Nephew, the content cannot be replicated, printed totally/partially or disclosed in any other way, and anyone must use it as per the requirements, either expressed or implied by Smith & Nephew.

Study Protocol - Device	Smith+Nephew
A Prospective, Multi-center, Randomized Clinical Study to Evaluate the Safety and Effectiveness of Biosure Regenesorb Interference Screw in Arthroscopic Reconstruction of Cruciate Ligaments in Chinese Patients	Study No.: BIOSURE RG.SMD.PMA.2019.01
	Version: V2.0/July 3rd, 2020
	Page 41 of 74

observations, or other activities used for study reconstruction and evaluation in clinical study).

Prior to the implementation of the clinical agreement, the Sponsor performs qualification evaluation visits to each study site to ensure that all investigators have received the corresponding training and that their personnel, facilities and resources are sufficient to carry out this study.

Before starting this study, the investigator must ensure that the following activities are completed and provide documentary records to the Sponsor.

10.3.1 Non-Disclosure Agreement

A Non-Disclosure Agreement (NDA) must be fully executed with the site and the Sponsor and any other appropriate parties.

10.3.2 Clinical Trial Agreement

A CTA must be fully executed by the site and the Sponsor and any other appropriate parties. Prior to initiation of the study, all investigators who will participate in the study need to be authorized by the principal investigator (PI), and the authorization outlines the responsibilities associated with the study. Unauthorized investigators are not allowed to participate in the study.

10.3.3 Ethical Approval

The protocol and informed consent materials must be approved by the EC at each institution. Copies of EC approval documents must be provided to the study Sponsor.

10.3.4 Documentation of Qualifications

A current, signed, dated CV and a current medical license for the principal Investigator and sub-Investigators must be submitted to the Sponsor prior to the study and in case of any update.

10.3.5 Monitoring visit by Sponsor

A site initiation visit will be performed by the Sponsor following the completion of the CTA negotiation and documented EC approval to provide training to the site on the specifics of the study and its conduct. The site must have written approval from the Sponsor before beginning enrollment.

Confidential and Proprietary

This document contains confidential and proprietary information on Smith & Nephew PLC and Smith & Nephew, Inc. and is only available to Smith & Nephew and its manufacturers. Without prior written approval of Smith & Nephew, the content cannot be replicated, printed totally/partially or disclosed in any other way, and anyone must use it as per the requirements, either expressed or implied by Smith & Nephew.

Study Protocol - Device	Smith+Nephew
A Prospective, Multi-center, Randomized Clinical Study to Evaluate the Safety and Effectiveness of Biosure Regenesorb Interference Screw in Arthroscopic Reconstruction of Cruciate Ligaments in Chinese Patients	Study No.: BIOSURE RG.SMD.PMA.2019.01
	Version: V2.0/July 3rd, 2020
	Page 42 of 74

The Sponsor may perform interim monitoring visits on a regular basis according to a schedule determined by the Sponsor. During these visits, the monitor will verify:

- Signed and dated informed consent forms
- Informed consent process occurred and is documented appropriately
- All inclusion/exclusion criteria were met
- Source documentation is complete and available
- Data on CRFs is verified by the source documentation
- Compliance with the protocol
- The reporting of adverse events occurred as required
- All required study documentation is complete and available

A monitoring visit will be performed by the Sponsor after the study closed to retrieve and account for all remaining clinical data and to resolve outstanding queries. During study close-out, the monitor will review the investigator files to ensure required documentation and records are on file, confirm the disposition of any other ancillary items used for the study, and review regulatory requirements regarding records retention and EC reporting requirements.

11 Data Management

Investigators will be provided with eCRFs based on the electronic data acquisition and management system to collect the data obtained during this study. The eCRFs include fields to record from source documentation specific information relative to the schedule of events. The investigator will complete a complete eCRF after each subject is included. The investigator will submit the completed PDF version of eCRF to the Sponsor.

Data quality procedures are designed to ensure that complete, accurate and timely data are submitted, that protocol requirements are followed, and that complications or adverse events are immediately identified and addressed until closure.

The Sponsor and study sites will promptly review all faxed eCRFs and accompanying documentation to identify inconsistent or missing data and device-related complications. Problems with these data will be addressed via online data queries. Investigators will resolve the queries or provide the Sponsor with information regarding the reasons for not resolving the query and an

Confidential and Proprietary

This document contains confidential and proprietary information on Smith & Nephew PLC and Smith & Nephew, Inc. and is only available to Smith & Nephew and its manufacturers. Without prior written approval of Smith & Nephew, the content cannot be replicated, printed totally/partially or disclosed in any other way, and anyone must use it as per the requirements, either expressed or implied by Smith & Nephew.

Study Protocol - Device	Smith+Nephew
A Prospective, Multi-center, Randomized Clinical Study to Evaluate the Safety and Effectiveness of Biosure Regenesorb Interference Screw in Arthroscopic Reconstruction of Cruciate Ligaments in Chinese Patients	Study No.: BIOSURE RG.SMD.PMA.2019.01
	Version: V2.0/July 3rd, 2020
	Page 43 of 74

expected resolution date.

To ensure the confidentiality of data, Smith & Nephew, Inc., the leading site and the authorizer will maintain a secure study database that maintains the confidentiality of study data.

Data quality is the basis for evaluating the clinical study results. Standardized data management helps to obtain true, accurate, complete and reliable high-quality data.

Clinical data management personnel should develop data management plan based on clinical trial protocol, specify and record data management tasks for the clinical trial, including personnel, roles, job contents, operation procedures, etc. in a detailed and comprehensive manner. The data management plan should be completed after the trial protocol is finalized and before the first subject is enrolled, which can be implemented only after the approval is obtained. Data management plans need to be updated and revised in time according to actual operations.

Each step of data management needs to establish and follow the corresponding standard operating procedures.

The design of the eCRF should guarantee the collection of all data which is specified in the trial protocol and meets the needs of statistical analysis. eCRF completion guidelines should be developed and training for investigators and CRC should be provided.

In the data management plan, a clear data flow should be established. The investigators should cooperate with the CRC to complete all eCRFs after the end of visit and respond after receiving the online data query, or provide information to the Sponsor to indicate the reason why the query has not been resolved and expected resolved date.

The data management department should formulate a detailed data verification plan before data verification, and define the data verification contents, methods and verification requirements.

Medical coding is the process of matching the descriptions of adverse events, medical diagnoses, concomitant medication, previous medication, previous medical history, etc. collected from the CRF with the terms in the standard dictionary. If medical coding is used, the coding process, coding tools, coding dictionaries and versions, as well as the relevant standard documents for performing the coding should be detailedly described in the data management plan.

The process of the database locking, the person in charge and the SOP file executed should be detailedly described in the data management plan.

When the database is locked, the unlocking and re-locking of the database should be specified in advance and the conditions and processes should be described in detail.

Confidential and Proprietary

This document contains confidential and proprietary information on Smith & Nephew PLC and Smith & Nephew, Inc. and is only available to Smith & Nephew and its manufacturers. Without prior written approval of Smith & Nephew, the content cannot be replicated, printed totally/partially or disclosed in any other way, and anyone must use it as per the requirements, either expressed or implied by Smith & Nephew.

Study Protocol - Device	Smith+Nephew
A Prospective, Multi-center, Randomized Clinical Study to Evaluate the Safety and Effectiveness of Biosure Regenesorb Interference Screw in Arthroscopic Reconstruction of Cruciate Ligaments in Chinese Patients	Study No.: BIOSURE RG.SMD.PMA.2019.01
	Version: V2.0/July 3rd, 2020
	Page 44 of 74

The trial data, the time of input/import into the database, the inputer, the data audit trail and the document formed in the data management process all need to be completely saved. The data formed in the data management process usually includes but is not limited to: clinical trial data, external data, database metadata information, laboratory test reference range, logical test and derived data change control list, electronic data query table, and program code, etc.. The files formed in the data management process usually includes but is not limited to: data management plan, blank eCRF, eCRF completion guide, PDF file of completed eCRF, annotated CRF, database design description, database entry description, data verification plan, data quality control verification report, etc.

The trial data, management files, media, archiving methods and time limits that need to be archived should be specified in the data management plan.

The data management department needs to determine the data as well as the quality control items, quality control methods (such as quality control frequency, sample selection method and sample size), quality requirements, qualification criteria and remedial measures for failure to meet the expected quality standards, etc. of data management operation process.

For data management work during and after the study, data manager should write data management report, summarize data management process, and present data management implementation procedures, SOP and management quality using qualitative and quantitative parameters.

The contents related to the data management implementation process, SOP and management quality should be fully and detailedly described in the data management report, including participating institutions/departments and responsibilities, major time nodes, CRF and database design, data verification and clean-up, medical coding, external data management, data quality assurance, data transfer records at key nodes, version change records of key documents and deviations from data management plan.

To ensure the confidentiality of data, the data management department will maintain the security of the study database and protect the confidentiality of study data.

12 Statistical considerations

12.1 Statistical design, method and analysis procedure

12.1.1 Statistical analysis principles

The statistical software SAS 9.4 or above is used for statistical analysis. The sample size is calculated using PASS 13. Adopt the trial results for endpoint analysis. FAS and PPS are used to

Confidential and Proprietary

This document contains confidential and proprietary information on Smith & Nephew PLC and Smith & Nephew, Inc. and is only available to Smith & Nephew and its manufacturers. Without prior written approval of Smith & Nephew, the content cannot be replicated, printed totally/partially or disclosed in any other way, and anyone must use it as per the requirements, either expressed or implied by Smith & Nephew.

Study Protocol - Device	Smith+Nephew
A Prospective, Multi-center, Randomized Clinical Study to Evaluate the Safety and Effectiveness of Biosure Regenesorb Interference Screw in Arthroscopic Reconstruction of Cruciate Ligaments in Chinese Patients	Study No.: BIOSURE RG.SMD.PMA.2019.01
	Version: V2.0/July 3rd, 2020
	Page 45 of 74

analyze primary and secondary outcomes while SS is used to analyze safety indicators.

Unless otherwise specified, all significance tests and hypothesis tests use a two-sided test at a significance level of 5%. When appropriate, the obtained p value will be cited and the two-sided 95% confidence interval will be generated. All p values will be rounded to three decimal places. In all tables, the p values less than 0.001 will be expressed as "<0.001".

Continuous variables will be summarized using summary statistics such as mean, standard deviation, median, minimum, maximum, lower quartile (Q1) and upper quartile (Q3), etc. Classified and ordinal variables are summarized using frequency and percentage.

For comparison of general conditions in two groups, an appropriate method will be adopted based on the indicator type to carry out analysis. Continuous indicators in two groups will be evaluated using a two-sample t-test (if data is normally distributed) or the Wilcoxon rank-sum test (if data is non-normally distributed). Classified data will be analyzed using a chi-square test or the Fisher's Exact Test (if the chi-square test is not applicable), and ranked data using the Wilcoxon rank-sum test or CMH test.

12.1.2 Completion and Demographic Analysis

Baseline Data

Demography and medical variables at baseline (including but not limited to, age, gender, race, medical history, medication history and disease diagnosis) will be used to describe subjects and summarize subject information. Summary statistics will be given based on the nature of variables (continuous or classified variables). For continuous variables, the number of observations, mean, standard deviation, median, minimum and maximum will be reported. For classified variables, the number of observations, frequency and percentage will be reported.

A detailed list of different data set sizes in each group, case distribution of each site, total dropout rate comparison and reasons for not completing the study, should be provided. The demographic characteristics (age, height, vital signs, etc.), the medical history and the medication history of the patients are described, and comparison of the age, height, body weight, etc. between the two groups will be conducted to measure the comparability between the two groups. The outcome data can be accepted and reported only when the baseline of two groups is balanced; otherwise, the outcome data needs to be corrected and then can be reported.

Confidential and Proprietary

This document contains confidential and proprietary information on Smith & Nephew PLC and Smith & Nephew, Inc. and is only available to Smith & Nephew and its manufacturers. Without prior written approval of Smith & Nephew, the content cannot be replicated, printed totally/partially or disclosed in any other way, and anyone must use it as per the requirements, either expressed or implied by Smith & Nephew.

Study Protocol - Device	Smith+Nephew
A Prospective, Multi-center, Randomized Clinical Study to Evaluate the Safety and Effectiveness of Biosure Regenesorb Interference Screw in Arthroscopic Reconstruction of Cruciate Ligaments in Chinese Patients	Study No.: BIOSURE RG.SMD.PMA.2019.01
	Version: V2.0/July 3rd, 2020
	Page 46 of 74

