Days for study	-30~-1	0~5	28-56	61-121	123-150	153-213	260-287	305-426	670-790
Informed consent	✓								
Inclusion/exclusion	✓	✓							
Demography/m edical history	✓								
Vital signs	✓	✓							
ECG	✓								
Blood routine examination	✓ ⁽¹⁾	✓ ⁽³⁾							
CRP	✓ ⁽¹⁾								
Blood biochemistry	✓ ⁽¹⁾	✓ ⁽³⁾							
Coagulation test	✓ ⁽¹⁾								
Pregnancy test [†]	✓								
Lysholm score	✓ ⁽¹⁾					✓ ⁽⁸⁾		✓ ⁽⁸⁾	✓ ⁽⁸⁾
IKDC score	✓ ⁽¹⁾					✓ ⁽⁸⁾		✓ ⁽⁸⁾	✓ ⁽⁸⁾
Drawer test	✓ ⁽¹⁾					✓		✓	✓
Lachman test	✓ ⁽¹⁾					✓		✓	✓
X-ray film	✓ ⁽²⁾	✓		✓ ⁽⁵⁾		✓		✓	✓
CT	✓ ⁽²⁾	✓		✓ ⁽⁵⁾		✓		✓	✓
MRI	✓ ⁽²⁾			✓ ⁽⁵⁾		✓		✓	✓
Randomization	✓ ⁽⁷⁾								
Operation		✓							
Telephone follow-up			✓	✓ ⁽⁶⁾	✓		✓		
Concomitant drug ⁽⁴⁾	✓	✓	✓	✓	✓	✓	✓	✓	✓
Adverse event	✓	✓	✓	✓	✓	✓	✓	✓	✓
Device Deficiency		✓	✓	✓	✓	✓	✓	✓	✓
Reoperation			✓	✓	✓	✓	✓	✓	✓
Study	✓	✓	✓	✓	✓	✓	✓	✓	✓

Confidential and Proprietary

This document contains confidential and proprietary information on Smith & Nephew PLC and Smith & Nephew, Inc. and is only available to Smith & Nephew and its manufacturers. Without prior written approval of Smith & Nephew, the content cannot be replicated, printed totally/partially or disclosed in any other way, and anyone must use it as per the requirements, either expressed or implied by Smith & Nephew.

Study Protocol - Device	Smith+Nephew
A Prospective, Multi-center, Randomized Clinical Study to Evaluate the Safety and Effectiveness of Biosure Regenesorb Interference Screw in Arthroscopic Reconstruction of Cruciate Ligaments in Chinese Patients	Study No.: BIOSURE
	RG.SMD.PMA.2019.01
	Version: V2.0/July 3rd, 2020
	Page 8 of 74

completion/with drawal										
---------------------------	--	--	--	--	--	--	--	--	--	--

- (1) For preoperative lab examinations and all scores, only those within Day 1~10 before the operation are acceptable.
- (2) If MRI, CT or X-ray film has been done within 30 days before the Informed Consent Form is signed, and the data are available, they can be used as the data for screening before operation.
- (3) It is tested before discharge.
- (4) All combination drugs associated with AEs or serious adverse events (SAEs) are reported.
- (5) Imaging examination 3 months after operation is optional.
- (6) Both telephone follow-up and follow-up visit to the hospital are acceptable.
- (7) Subjects are randomized after signing of ICF but before anesthesia begins.

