10.2.2.2 Pre-operative study activities

Prior to the operation, the following information must be collected:

Confidential and Proprietary

This document contains confidential and proprietary information on Smith & Nephew PLC and Smith & Nephew, Inc. and is only available to Smith & Nephew and its manufacturers. Without prior written approval of Smith & Nephew, the content cannot be replicated, printed totally/partially or disclosed in any other way, and anyone must use it as per the requirements, either expressed or implied by Smith & Nephew.

Study Protocol - Device	Smith+Nephew
A Prospective, Multi-center, Randomized Clinical Study to Evaluate the Safety and Effectiveness of Biosure Regenesorb Interference Screw in Arthroscopic Reconstruction of Cruciate Ligaments in Chinese Patients	Study No.: BIOSURE RG.SMD.PMA.2019.01
	Version: V2.0/July 3rd, 2020
	Page 35 of 74

- Demographics include:
 - Age at surgery (calculated from date of birth)
 - Gender (male/female)
 - Occupation
 - Height (in cm) and body weight (in kg)
 - Body mass index (BMI)
- Vital signs: pulse, blood pressure, respiration and body temperature
- Physical examination status
- Medical history will be obtained and will include:
 - Previous medical history (HEENT, respiratory, gastrointestinal, hematological, cardiovascular, endocrine/metabolic, musculoskeletal, immunological, neurological, genitourinary, prior surgery, others)
 - Tobacco use and alcohol intake (tobacco use: never used, past use, current use; alcohol intake)
 - Closure of epiphyseal plate
 - Current medical history of knee diseases: time of knee injury, cause of knee injury, conditions of the studied knee side (left/right) and the contralateral knee joint, cause of CL rupture or tear, other combined knee injury, knee degeneration and whether or not to totally excise the medial or lateral meniscus
 - Previous surgeries on the affected knee joint (For surgery history, fracture fixation, arthroscopy, ligament surgery, autologous cell transplantation or other surgery, please specify)
 - Safety events
 - All combination drugs associated with AEs or SAEs are recorded.

In addition, subjects will be evaluated clinically pre-operatively using:

- Lysholm Score
- IKDC Score
- Drawer test

Confidential and Proprietary

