12.1.3 Primary efficacy endpoints

Primary efficacy evaluation will be based on Full Analysis Set (FAS) and Per-Protocol Set (PPS). For the statistical description and inference of the data, the applicable descriptive endpoints and hypothesis testing methods will be selected based on the characteristics of the data.

The primary efficacy endpoint of this study is Lysholm score at 12 months after operation. The non-inferiority testing is performed for efficiency of primary efficacy endpoint, and the test hypothesis is as follows:

Invalid hypothesis: $H_0: \mu_1 - \mu_2 \leq -\delta$

Alternative hypothesis: $H_1: \mu_1 - \mu_2 > -\delta$,

where, μ_1 and μ_2 are the Lysholm scores in the investigational group and control group, respectively. δ is a non-inferiority critical value. At $\alpha=0.025$ (one-sided test), the hypothesis test is carried out using a two-sided t-test. A non-inferiority test is carried out on the Lysholm scores in the investigational group and control group. The 95% confidence interval between the two groups is calculated.

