12.5 Criteria for acceptability/unacceptability of clinical trial result

Primary efficacy endpoint (the Lysholm score at 12 months after operation): If the lower limit of 95% CI for the efficacy difference between two groups is greater than the non-inferiority margin, it is considered that the investigational product is non-inferior to the control product, the statistical hypothesis is valid and the result of clinical trial is qualified; otherwise, the hypothesis is invalid, and the result of clinical trial is unacceptable.

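### Whether the primary non-inferiority estimate is adjusted depends on an undefined baseline balance check, and the pre-operative Lysholm score is not pre-specified as a covariate

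*Combined protocol and SAP*

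**What the plan says.** Section 12.1.2 (Completion and Demographic Analysis) provides that "comparison of the age, height, body weight, etc. between the two groups will be conducted to measure the comparability between the two groups". It then sets a condition on the results: "The outcome data can be accepted and reported only when the baseline of two groups is balanced". For the case where this condition fails, the section offers a single instruction and no method: "otherwise, the outcome data needs to be corrected and then can be reported".

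Section 12.1.1 names tests for comparing the groups' general conditions (t-test or Wilcoxon, chi-square or Fisher, Wilcoxon or CMH) and a default two-sided 5% level. It does not say that a p-value below 0.05 makes the groups unbalanced.

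Section 12.1.3 gives the primary analysis of month-12 Lysholm: "the hypothesis test is carried out using a two-sided t-test", with a 95% CI and no covariate. Section 12.5 decides the trial on one interval: "If the lower limit of 95% CI for the efficacy difference between two groups is greater than the non-inferiority margin".

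The pre-operative Lysholm score is a scheduled assessment. It is listed in section 10.2.2.2 and ticked in the Study follow-up schedule, where footnote (1) adds: "For preoperative lab examinations and all scores, only those within Day 1~10 before the operation are acceptable".

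**The concern.** Taken together, these sections leave open which estimate decides non-inferiority. If someone judges baseline to be unbalanced, 12.1.2 replaces the 12.1.3 t-test with a correction that has no stated trigger, covariates or model. Section 12.5 does not say which interval then counts. Whether the deciding estimate is adjusted therefore depends on the observed baseline data and on a judgement the plan does not define. This estimate supports the registration claim.

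The collected baseline value of the endpoint itself is named neither in the balance comparison nor in the primary test. A chance difference in it that nobody declares stays in the estimate, and the precision it could supply is not used.

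**Working it through.** **Inputs from section 12.2.1.** Margin 5, true difference 0, one-sided alpha 0.025, power 0.80, 20% drop-out, 70 randomized per group. The text calls 9 the variance, but only SD = 9 gives the stated sample size.

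**Plan's own figure.** n = 2 × (1.960 + 0.842)² × 81 / 25 = 50.9, so 51 per group, and 51/0.80 = 63.75, so 64. Both reproduce. The evaluable number at the planned size is 70 × 0.80 = 56 per group.

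**Assumed.** The correlation rho between pre-operative and month-12 Lysholm is not in the documents; 0.2, 0.3 and 0.5 are shown. No trigger for correction is stated either; the simulations assume a baseline Lysholm t-test with p < 0.05.

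**Analytic power at 56 per group.** Noncentral t with residual SD = 9 × √(1 − rho²) gives 83.0% unadjusted, and 84.5% / 86.3% / 92.0% for ANCOVA.

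**Simulation.** Bivariate normal data, 400,000 trials per cell, 56 per group:

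| | rho 0.2 | rho 0.3 | rho 0.5 |
|---|---|---|---|
| Power, ANCOVA always | 84.1% | 85.9% | 91.7% |
| Power, adjust only if baseline p < 0.05 | 83.1% | 83.2% | 83.9% |
| Adjusted and unadjusted verdicts differ, true difference 0 | 4.1% | 6.4% | 11.2% |
| One-sided type I error, fixed conditional rule | 0.025 | 0.024 | 0.022 |
| One-sided type I error, if either analysis may be used | 0.030 | 0.032 | 0.037 |

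Simulated ANCOVA power is about 0.3 to 0.4 points below the analytic value, because the slope has to be estimated. It is the like-for-like comparison with the conditional rule. The last row is an upper bound that applies only if the choice is made after both results are seen.

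**Shift left in the estimate by an undeclared Lysholm imbalance.**
- Just at p = 0.05: rho × 9 × 1.96 × √(2/56) = 0.67 / 1.00 / 1.67 points, in either direction.
- Average absolute shift among imbalances that pass a 5% check: 0.717 × rho × 9 × √(2/56) = 0.24 / 0.37 / 0.61 points, or 5% / 7% / 12% of the margin. Here 0.717 is the mean of |Z| given |Z| < 1.96.

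**How the open variable list matters.** If unbalanced meant any baseline p < 0.05, correct randomization with k independent tests would trigger correction with probability 1 − 0.95^k: 14.3% for 3 variables, 40.1% for 10 and 64.2% for 20.

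**The case against.** - **Section 12.1.1 may supply the rule.** It does name baseline tests and a 5% default, so a p < 0.05 threshold is a natural reading. It still does not say which variables count, how to correct, or which interval decides in 12.5.
- **Pre-operative Lysholm is not excluded.** True: the 12.1.2 list is open-ended. That is part of the difficulty, since the list affects how often correction is triggered.
- **The 4 / 6 / 11% disagreement overstates what the balance clause does.** This stands as a limit. That figure compares the two analyses in all trials. With a trigger on Lysholm alone at p < 0.05, correction is triggered and changes the verdict in only about 0.6% to 1.4% of trials. Other triggering variables would make correction more frequent, but that was not simulated.
- **The FAS uses LOCF, so it may approach 70 per group.** At 70, if carried-forward values keep the planning SD, power is 90.4% unadjusted and 91.5% / 92.8% / 96.5% with ANCOVA (noncentral t). Disagreement falls to about 3% / 4% / 7%. The gain is smaller but in the same direction.
- **ANCOVA needs the covariate.** A pre-operative score outside the Day 1~10 window could leave it missing. Also, 12.9.1 does not bar a pre-operative score from being carried forward as the outcome. Both need a sentence in the plan; neither is a reason against the model.
- **A statistical analysis plan might settle the matter.** Section 12.7 mentions one, but the text says both that it is developed before the trial and that it is issued after database lock. Nothing supplied fixes the choice.

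**Conclusion.** The concern holds. The rule that decides whether the primary estimate is adjusted is undefined, at any value of rho. The precision loss depends on rho: at 56 per group it is about 1 power point at 0.2, 3 at 0.3 and 9 at 0.5. A test-then-adjust rule on baseline Lysholm recovers almost none of it.

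The limits are equally clear. The unadjusted t-test is valid and exceeds the 80% target, the sample size is not in question here, and a fixed conditional rule does not inflate type I error. The 0.030 to 0.037 range requires picking the analysis after seeing both results, which the plan does not say will happen. The change should be made because it removes discretion over the deciding result at almost no cost. All figures rest on SD 9, normal data, and the assumed rho and trigger.

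**What to change.** - **12.1.3:** name one primary model, ANCOVA of month-12 Lysholm on treatment and pre-operative Lysholm. If site is wanted as a factor, write it into the model now. Keep the unadjusted t-test as a sensitivity analysis.
- **12.5:** state that the two-sided 95% CI comes from that model, in FAS and PPS, whatever the baseline tables show.
- **12.1.2:** delete the sentence that makes acceptance and correction depend on balance, and keep the baseline tables descriptive.
- **Missing values:** add a line on a missing or out-of-window pre-operative score, and say whether such a score may be carried forward as the month-12 outcome.

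The cost is wording in these sections and one SAS model statement. No new data, visits or subjects are needed.
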